Adaptive Design: The Steering and Safety Committee and Sponsor will review the accumulating efficacy and safety data at planned intervals, and based upon the safety and efficacy profile of SelK2 may decide to modify enrollment by adding a third study arm testing 7.5 mg/kg SelK2 given in addition to enoxaparin (40 mg, SC, QD) and removal of the SelK2 only arm. The two remaining arms will enroll patients in a 2:1 ratio with two patients receiving SelK2 and Enoxaparin for every one patient receiving Enoxaparin only at doses shown below:

- 1.) 7.5 mg/kg SelK2 (IV, single-dose) and 40 mg Enoxaparin, SC, QD
- 2.) Active Comparator (40 mg Enoxaparin, SC, QD)

Criteria for Selection of Patients:*Inclusion Criteria:*

1. Males or females, between 18 and 80 years of age, inclusive;
2. Females must be non-pregnant and non-lactating, and either postmenopausal (>12 months since last menses) or using highly effective contraceptive measures as defined by the Clinical Trial Facilitation Group (CTFG) guidelines;
3. Males, if engaged in sexual relations with a partner of child-bearing potential, must use highly effective contraceptive measures as defined by the Clinical Trial Facilitation Group (CTFG) guidelines;
4. Planned to undergo elective, primary total unilateral TKA under general anesthesia; and
5. Able to comprehend and willing to give written informed consent.

Exclusion Criteria:

Patients presenting with any of the following will not be included in the study:

1. Body weight <50 kg at Screening;
2. Previous deep vein thrombosis (DVT) of the leg or pulmonary embolism (PE) within the past year;
3. Malignancy within 1 year, except for basal or squamous cell carcinoma of the skin or carcinoma *in situ* of the cervix that has been successfully treated;
4. Myocardial infarction, transient ischemic attack or stroke within the last 6 months;
5. Patients at increased risk of bleeding because of history of increased bleeding tendency (i.e., history of bleeding diathesis) or any other condition that in the opinion of the Investigator increases risk of bleeding (e.g., recurrent gastrointestinal ulcer) or patients with a history of intracranial or intraocular bleeding;
6. Brain, spinal, or ophthalmologic surgery within the past 3 months;
7. Cockcroft-Gault calculated creatinine clearance <30 mL/min at Screening (central lab will calculate the Cockcroft-Gault value);

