1.5 Rationale for the Dose Regimen

2.0 STUDY OBJECTIVES

The objectives of this study are:

Primary:

- To investigate the efficacy of SelK2 as monotherapy for the prevention of VTE (composite of asymptomatic DVT detected by mandatory unilateral venography of the operated leg or confirmed symptomatic DVT, confirmed symptomatic PE or unexplained death) in patients undergoing primary unilateral TKA.
- To assess the incidence of bleeding events (major bleeding events, clinically relevant non-major bleeding events, and minor bleeding events) in patients administered SelK2 and undergoing primary unilateral TKA.
- To assess the overall safety and tolerability of SelK2 in this patient population.

Secondary:

- To further describe the PK and PD of SelK2.
- To evaluate the immunogenicity of single dose SelK2.
- To evaluate exploratory efficacy endpoints of inflammation and thrombosis.

Adaptive Arm (SelK2 given concomitantly with enoxaparin; SelK2, 7.5 mg/kg, IV and enoxaparin, 40 mg, SC, QD):

- Assess the efficacy and safety of SelK2 when given in addition to enoxaparin for the prevention of VTE in patients undergoing primary unilateral TKA.

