10.0 STATISTICAL METHODS AND PLANNED ANALYSES

10.1 Sample Size and Power

Assuming that the rate of VTE for the active comparator (enoxaparin) arm of this study will be 25%, it is estimated that a sample size of 76 evaluable patients per arm should give the study 80% power of declaring non-inferiority between the SelK2 arm and the enoxaparin active comparator arm. This calculation uses a one-sided 90% CI with a non-inferiority margin of 15%. This calculation assumes that the underlying rate of VTE for the SelK2 and enoxaparin arms will be identical at 25% and with the non-inferiority margin set as at the midpoint between the expected active therapy response compared to an assumed placebo event rate in this patient population of 55%. Consequently, making the conservative estimate that up to 20% of randomized patients may not yield evaluable endpoint data, a total of 95 patients will be enrolled per arm to provide at least 76 endpoint evaluable patients per arm.

Sample Size Considerations for Adaptive Arm:

With the same assumptions as above the for active comparator (enoxaparin) arm of the study event rate, it is estimated that a sample size of 76 evaluable patients in a combination therapy arm of SelK2 and enoxaparin should give the study 80% power of declaring superiority between the SelK2 and enoxaparin arm and the enoxaparin active comparator arm for an estimated SelK2 and enoxaparin VTE event rate of 6% (an 19% difference between combination treatment effect and active comparator treatment effect). This calculation assumes a two-sided 0.1 alpha, a Pearson Chi-squared test, and a superiority comparison.

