10.3.3 Efficacy Analyses

For all efficacy analyses, the main analysis will be based on the mITT population. Both primary and secondary endpoint analyses will also be performed on the PP population; these analyses will be supportive only. Comparisons will be made between the SelK2 treated patients SelK2 and enoxaparin treated patients, and the enoxaparin group. The difference of the total VTE rate during the Treatment Phase (from time of randomization up until the day of completion of venogram) between the SelK2, SelK2 and enoxaparin, and enoxaparin treatment groups will be estimated. The lower 1-sided 90% CI of the difference will be calculated and non-inferiority will be concluded if the upper limit of the 90% CI is $\leq 15\%$. The same analysis will be completed on the PP population.

The following secondary analyses will be performed on the mITT and PP populations:

- Comparison of the rates of the individual components of the primary efficacy outcome between the SelK2, SelK2 and enoxaparin, and enoxaparin treatment groups through Treatment Period.
- Conduct primary efficacy analysis of the total VTE rate between the SelK2 treatment, SelK2 and enoxaparin treatment, and enoxaparin treatment with the inclusion of events through Study Day 57.
- Complete comparison of the rates of the individual components of the primary efficacy outcome between the SelK2, SelK2 and enoxaparin, and enoxaparin treatment groups with the inclusion of events through Study Day 57.

Absolute changes from baseline in hsCRP and D-dimer will be summarized by treatment group at each post-baseline visit. Change from baseline in each parameter will be analyzed and compared between treatment groups using a mixed linear model with repeated measures (MMRM).

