10.5 Steering and Safety Committee Data Reviews and Interim Analyses

A formal study Steering and Safety Committee will consist of at least 3 clinicians (with experience and expertise in venous thrombosis). The Steering and Safety Committee will be charged with reviewing in an unblinded fashion all accumulating safety and efficacy data to assure overall patient safety in this study.

The following efficacy and safety data will be provided to the Steering and Safety Committee by treatment group, and where appropriate by study visit day and time:

- Overall VTE event rate (as adjudicated);
- Individual component event rate (individual components of the composite VTE event rate);
- Incidence of bleeding events (as adjudicated) including the following will be tabulated by treatment:
 - 1) Major Bleeding event (MB),
 - 2) Clinically Relevant Non-Major Bleeding event (CRNMB),
 - 3) Minor Bleeding even, or
 - 4) Combination of MB and CRNMB
- Incidence of AEs (including SAEs) ;
- Clinical laboratory values (hematology, serum chemistries, urinalysis, and coagulation parameters);
- ECGs; and
- Vital signs.

The Steering and Safety Committee will use all of the above accumulating data to assess the safety of continuing each aspect of this study.

Interim Analyses to support decision on whether or not to recommend activation of Adaptive Arm:

The Steering and Safety Committee is also charged with making recommendations to the Sponsor with regards to the activation of the adaptive arm that investigates the efficacy and safety of SelK2 use in combination with enoxaparin. At certain enrollment milestones, the Steering and Safety Committee will be presented with interim analysis tables which will include VTE event rates by treatment group with 80% confidence intervals and the calculated risk difference (the difference

between the cumulative incidence in the SelK2 arm to that of the cumulative incidence the enoxaparin arm) with 80% confidence intervals. The conditional powers for demonstrating non-inferiority at the end of the trial based upon accumulated data at interim may also be computed. These interim analyses will be part of the data set used by the Committee as they determine whether or not to recommend activation of adaptive arm. This adaptive arm may be initiated if the Steering and Safety Committee determines that preliminary data suggests the potential for an additive effect in VTE reduction and that the combination does not pose an additional safety risk.

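### The stated 80% non-inferiority power for SelK2 alone holds only if that arm completes enrolment; activating the adaptive arm closes it early, to about 59–68% power at one half, and the plan does not say so

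*Combined protocol and SAP*

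**What the plan says.** Section 2.0 puts SelK2 alone first among the primary objectives: "To investigate the efficacy of SelK2 as monotherapy for the prevention of VTE". Section 10.1 sizes the trial for it: "a sample size of 76 evaluable patients per arm should give the study 80% power of declaring non-inferiority between the SelK2 arm and" the enoxaparin arm. Allowing for 20% non-evaluable, that becomes 95 enrolled per arm. The synopsis repeats this.

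The amended synopsis (Adaptive Design) allows a third arm testing SelK2 "given in addition to enoxaparin (40 mg, SC, QD) and removal of the SelK2 only arm". Section 5.1.3 confirms that SelK2-only is closed when the adaptive arm opens. Later patients are randomised 2:1 to the combination or enoxaparin, so that these two arms finish at about the same size.

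The statistical text does not follow the change through. Section 10.1 attaches no condition to the 80%. Sections 3.2 and 4.0 provide for 95 more patients on top of 190, and Section 3.2 puts the maximum at about 285. Section 10.3.3 applies one rule throughout: "The lower 1-sided 90% CI of the difference will be calculated and non-inferiority will be concluded if the upper limit of the 90% CI is" no more than 15%. No section gives the size or power of a closed SelK2-only arm, or says whether enoxaparin patients randomised after closure count as its controls. Section 10.5 speaks only of enrolment milestones for the interim review, without numbers.

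**The concern.** Activation is a path the protocol itself plans, and on that path the arm carrying the first primary objective stops short of the size that earned the 80%. A reader of Section 10.1 would credit the trial with power it does not have there. Two consequences follow.

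- With fewer patients the confidence limit sits further above the estimate. The same 15% rule is then harder to meet when SelK2 is truly as good as enoxaparin, and a miss says less about SelK2 than it would in a full arm.
- Closure follows a committee review of unblinded VTE rates by arm. The chance of wrongly concluding non-inferiority is therefore no longer fixed at 10%. It depends on a closure rule the plan does not state.

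**Working it through.** **Inputs, all from Section 10.1.** Enoxaparin rate: "Assuming that the rate of VTE for the active comparator (enoxaparin) arm of this study will be 25" per cent. SelK2 rate: "underlying rate of VTE for the SelK2 and enoxaparin arms will be identical at 25" per cent. Error and margin: "This calculation uses a one-sided 90% CI with a non-inferiority margin of 15" per cent. Evaluable per arm: 76.

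**Formula.** SE = √[0.25 × 0.75 × (1/n_S + 1/n_E)] = √[0.1875 × (1/n_S + 1/n_E)]. Power = Φ(0.15/SE − 1.2816). The upper limit lies 1.2816 × SE above the estimate; this is the half-width below.

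**The plan's own figure.** 76/76: SE = √(0.1875 × 2/76) = 0.0702; 0.15/0.0702 = 2.135; 2.135 − 1.282 = 0.854; Φ = 80.3%. Exact enumeration of the Wald rule gives 80.6%. The stated 76 per arm reproduces, and 76/0.8 = 95.

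**Closure point implied by the current text.** Let E be the enoxaparin enrolment at the switch and C the final combination arm. Under 2:1, C/2 more enoxaparin patients enter. Equal final arms require E + C/2 = C, so E = C/2. With C = 95, E = 47.5. Allocation before the switch is 1:1, so SelK2-only also stops at about 47.5 randomised, or 0.8 × 47.5 = 38 evaluable. The total is 47.5 + 95 + 95 = 237.5, not 285.

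**If 285 is kept instead.** C/2 + C + C = 285 gives C = 114 and SelK2-only 57, i.e. about 46 evaluable against 91.

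| SelK2-only closed at | n_S / n_E evaluable | Power | Half-width (points) |
|---|---|---|---|
| Not closed | 76 / 76 | 80.3% | 9.0 |
| One half, concurrent controls | 38 / 38 | 59.0% | 12.7 |
| One half, all controls | 38 / 76 | 67.8% | 11.0 |
| 57 randomised (285 kept), concurrent | 46 / 46 | 64.8% | 11.6 |
| 57 randomised (285 kept), all | 46 / 91 | 73.7% | 10.0 |
| One third (assumed), concurrent | 25 / 25 | 47.7% | 15.7 |
| One third (assumed), equal final arms | 25 / 51 | 55.5% | 13.5 |
| One third (assumed), full enoxaparin arm | 25 / 76 | 58.7% | 12.8 |
| Two thirds (assumed), concurrent | 51 / 51 | 68.0% | 11.0 |
| Two thirds (assumed), planned 76 controls | 51 / 76 | 73.6% | 10.0 |

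In the 25/51 row, about 32 are randomised per arm at the switch. Under 2:1, equal final arms are then about 64 each, and 0.8 × 64 ≈ 51. At 25/25 the half-width exceeds 15 points, so equal observed rates near 25% would miss the limit.

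**Error rate after an unblinded closure (illustrative, because the plan states no rule).** Simulation at a true 40% versus 25%, i.e. at the margin, with the Wald limit. Interim look at 25 or 38 evaluable per arm. d is the observed SelK2-minus-enoxaparin difference. If the arm is not closed, both arms go to 76.

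| Closure rule | False non-inferiority, concurrent controls | Against all 76 |
|---|---|---|
| No closure | 9.9% | – |
| Favourable: close if d ≤ 0 or d ≤ 5 points | 13.6–15.1% | 12.0–13.6% |
| Unfavourable: close if d > 0 or d > 5 points | 5–6% | 8–9% |

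**The case against.** Several objections have force.

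**Timing.** A reader might take one third to one half as the planned closure window. The 33%–50% range stands only in superseded wording in the list of modifications, so it cannot be held against the current plan. What the current text supports is closure near one half, by inference from the 2:1 aim and only if the remaining arms reach 95.

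**Loss of the primary question.** A reader might infer that the trial most likely cannot answer its monotherapy question once the arm closes. The figures do not support that: every scenario in the table except 25 against 25 keeps power above 50%. They are also fixed-sample figures. If closure follows a favourable result, much of the loss disappears: under the two favourable rules at 38 per arm with concurrent controls, overall power at equal true rates is about 83% and 79%.

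**Error inflation.** A reader might infer that false non-inferiority rises to 14–15%. That needs closure after a favourable result and concurrent controls. The stated trigger, a possible additive effect without added safety risk, does not fix the direction, and closure after a disappointing result lowers the error.

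**Conditional power.** Section 10.5 says "The conditional powers for demonstrating non-inferiority at the end of the trial based upon accumulated data at interim may also be computed". It is tempting to call this misleading, since activation ends the arm it describes. But the figure is optional and does bear on whether to stop that arm, and presentation details are left to a charter not available here.

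**The unchanged rule.** Keeping the 15% limit at a smaller size is not an error, because the interval widens by itself. Section 10.3.3 says when non-inferiority is concluded; it does not say that a miss is reported as failure.

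What remains is that the 80% is stated without a condition it needs, and the control set after closure is unnamed.

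**Conclusion.** The point holds as a mismatch between the amended design and the statistical text. On the adaptive path SelK2-only stops before 95 patients, and the stated 80% does not apply to it as a fixed-sample figure. At closure near one half, power is about 59% with concurrent controls and 68% with all 76. If one third or two thirds is assumed instead, it is about 48–59% or 68–74%. If 285 is kept with equal remaining arms, it is about 65–74%. The 285 total equals three full arms and does not fit closure near one half with the other two arms at 95.

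These figures rest on the plan's 25% rates, its 15-point margin and a normal approximation, with closure treated as unrelated to the data. The 10% error rate also becomes dependent on the unstated closure rule: about 12–15% after a favourable result and 5–9% after an unfavourable one, under illustrative rules. That is a reason to state how closure is handled; it does not show that error is inflated. Activation is optional, and without it the 80% stands.

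**What to change.** - **Section 10.1 and synopsis:** state that the 80% applies only if SelK2-only completes enrolment. Add a small table of power and interval half-width by closure point (for example one third, one half, two thirds).
- **Sections 3.2 and 4.0, and the synopsis patient number:** reconcile the 285 total with closure of the arm and the 2:1 ratio.
- **Section 10.3.3:** name concurrently randomised enoxaparin patients as the control set for SelK2-only after early closure. Report the risk difference with its interval, and state that a missed 15% limit in a truncated arm is inconclusive. Making that comparison estimation only, with no non-inferiority claim, is an option for the sponsor and not a necessary correction.

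The cost is wording and one table, with no extra patients. The downside is that the stated power on the adaptive path looks less favourable. Using concurrent controls also gives the lower power of the two control sets (59% rather than 68% at one half), in exchange for comparing patients randomised over the same period.

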Other safety evaluations will include assessment of adverse events, physical examinations, 12-lead ECGs, vital signs (including temperature, respiratory rate, and seated blood pressure and pulse), clinical chemistry laboratory evaluations, additional laboratory evaluations including prothrombin time/international normalized ratio (PT/INR), activated partial thromboplastin time (aPTT), hematology panel, urinalysis, and pregnancy test (female patients of child bearing potential only).

Statistical Methods:

Demographic and other patient data will be summarized by treatment group using descriptive statistics.

The primary efficacy comparison will compare the SelK2 only-treated, SelK2 and enoxaparin-treated, and enoxaparin only-treated arms. The difference in the total VTE rate determined during the entire Treatment Phase will be estimated. The 1-sided lower 90% CI of the difference between the SelK2 and enoxaparin groups only arms as well as the difference between the adaptive arm (SelK2 and enoxaparin) and enoxaparin only arms will be calculated and non-inferiority will be concluded if the upper limit of the 90% CI is $\leq 15\%$. Absolute changes from baseline in levels of high-sensitivity CRP and D-dimer will be assessed. A number of secondary analyses may be conducted to assess the robustness of the primary analysis finding.

SelK2 concentrations will be summarized by descriptive statistics.

Safety will be assessed by reported adverse events, changes from baseline during treatment in vital signs, ECGs, laboratory parameters, and physical examination and will be summarized using descriptive statistics. Adverse events will be coded using the (Medical Dictionary for Regulatory Activities) MedDRA dictionary and summarized by system organ class, preferred term, Investigator causality assessment, and treatment group. Incidence of bleeding events (as adjudicated by CIAC) will be tabulated by treatment group.

Sample Size Considerations:

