1.4 Study Rationale

Venous thromboembolism is a major medical burden affecting millions of people around the world, with approximately one million cases and 300,000 deaths annually in the United States and approximately 1.5 million cases and 540,000 deaths annually in the European Union.

Approved therapies and standard of care available for use in VTE target the coagulation system and can therefore result in major bleeding events leading to significant morbidity and mortality. There is a continuing medical need for the development of novel antithrombotic agents, especially those that may operate through a unique mechanism of action which are not associated with an increase in bleeding risk.

This randomized, active comparator-controlled, open-label study is being conducted to determine the efficacy and safety of SelK2 when administered once to patients undergoing primary unilateral total knee arthroplasty. The study will compare the efficacy and safety of SelK2 to the standard of care, enoxaparin. The primary endpoint to assess clinical efficacy will be the composite of asymptomatic DVT, detected by mandatory unilateral venography, and objectively confirmed symptomatic VTE during the treatment phase of the study. The primary safety outcome is a combination of major bleeding events and clinically relevant non-major bleeding events during the treatment phase.

This study includes an adaptive arm that investigates the efficacy and safety of SelK2 use in combination with enoxaparin. This adaptive arm may be initiated if the Steering and Safety Committee determines that preliminary data suggests the potential of an additive effect in VTE reduction and that the combination does not pose an additional safety risk. The data obtained from this Phase 2 study will be used to provide evidence to support the claim of efficacy and safety of SelK2 in this patient population.

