10.3 Statistical Analysis

10.3.1 General Considerations

Descriptive summary statistics include mean, median, standard deviation, interquartile range, and range (minimum, maximum) for continuous variables, and counts and percentages for categorical

variables. Unless otherwise specified, continuous variables will be analyzed using two-sample t-test or Wilcoxon-Mann-Whitney test, whichever is appropriate; and categorical variables will be analyzed using chi-squared test or Fisher's exact test, whichever is appropriate.

SAS 9.3 or later will be used to perform statistical analysis. Unless otherwise specified, a two-sided p-value less than 0.05 will be considered statistically significant. No multiplicity adjustment will be made.

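### The Synopsis and Section 10.3.3 put two contrasts under the primary comparison, although Section 2.0 makes only SelK2 monotherapy the primary efficacy objective, so a combination-only result could be reported as primary success.

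*Combined protocol and SAP*

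**What the plan says.** **Objectives.** The primary efficacy objective in Section 2.0 is "To investigate the efficacy of SelK2 as monotherapy for the prevention of VTE". Efficacy and safety of the combination stand under a separate adaptive-arm heading.

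**Analysis.** The Statistical Methods part of the Synopsis reads: "The primary efficacy comparison will compare the SelK2 only-treated, SelK2 and enoxaparin-treated, and enoxaparin only-treated arms". After the SelK2 versus enoxaparin difference it continues: "as well as the difference between the adaptive arm (SelK2 and enoxaparin) and enoxaparin only arms will be calculated and non-inferiority will be concluded". The condition is a 90% limit no greater than 15%. Section 10.3.3 applies the same rule to the three groups: "Comparisons will be made between the SelK2 treated patients SelK2 and enoxaparin treated patients, and the enoxaparin group". Its Day 57 secondary analysis again treats the three-group comparison as primary: "Conduct primary efficacy analysis of the total VTE rate between the SelK2 treatment, SelK2 and enoxaparin treatment, and enoxaparin treatment".

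**Multiplicity.** Section 10.3.1 states: "No multiplicity adjustment will be made". No section gives a testing order, an alpha split or a deciding contrast.

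**Sample size.** Section 10.1 sizes monotherapy for non-inferiority at one-sided 10%: 25% VTE in both arms, a 15-point margin, 80% power, 76 evaluable and 95 enrolled per arm. It sizes the combination for superiority with a Pearson chi-squared test at two-sided 0.1. Section 10.3.3 contains no superiority test.

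**Adaptation.** Section 5.1.3 closes the SelK2-only arm on activation and then randomizes 2:1, so that the combination and enoxaparin arms finish about equal in size.

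**The concern.** The objectives and the analysis text disagree on what is primary. Suppose the adaptive arm opens, monotherapy fails its bound and the combination passes. Under Section 2.0 the primary efficacy objective is not met. Under the Synopsis and Section 10.3.3 a primary comparison has succeeded.

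The two results mean different things. The combination patients receive the full enoxaparin regimen, so being no more than 15 points worse than enoxaparin says little about whether SelK2 works. If SelK2 added nothing to enoxaparin (25% in both arms, 76 per arm), the combination would still meet the written rule about 81% of the time. That would be a true non-inferiority conclusion, but it is not evidence for SelK2. Section 1.4 says the data "will be used to provide evidence to support the claim of efficacy and safety of SelK2 in this patient population", so it matters which contrast carries the claim.

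There is also an error-rate question. The 76 per arm rests on a one-sided 10% error for one contrast, and that figure need not describe two primary contrasts that are each tested at 10%.

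**Working it through.** **1. The plan's own figure.** Inputs from Section 10.1: rates 25% and 25%, margin 0.15, one-sided alpha 0.10, power 0.80.

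n = (z₀.₉₀ + z₀.₈₀)² × 2 × 0.25 × 0.75 / 0.15² = (1.2816 + 0.8416)² × 0.375 / 0.0225 = 75.1, so 76 per arm. Enrolment is 76 / 0.80 = 95.

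Both stated figures reproduce. One-sided 5% would need 104, so the design level is one-sided 10% for a single contrast.

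**2. Upper case, normal approximation.** Put both regimens at the margin (40% versus 25%), with 76 evaluable in each of three arms and a shared control. The correlation of the two differences is

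ρ = (0.25 × 0.75) / (0.25 × 0.75 + 0.40 × 0.60) = 0.1875 / 0.4275 = 0.44.

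The chance of at least one false conclusion is 1 − Φ₂(1.2816, 1.2816; 0.44) = 17.1%. With no shared controls it is 1 − 0.90² = 19.0%.

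**3. Exact binomial enumeration.** This uses the Wald one-sided 90% upper limit against 15 points, with 76 enoxaparin and 76 combination patients. The SelK2-only size at closure is not stated, so 51, 38 and 25 are assumptions. The power column sets SelK2 alone and enoxaparin both at 25%.

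| SelK2-only evaluable | False monotherapy conclusion | False combination conclusion | At least one | Monotherapy power |
|---|---|---|---|---|
| 76 | 9.9% | 9.9% | 17.2% | 80.6% |
| 51 | 10.3% | 9.9% | 17.7% | 73.4% |
| 38 | 10.8% | 9.9% | 18.4% | 68% |
| 25 | 11.5% | 9.9% | 19.2% | 59.7% |

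**4. Only monotherapy inferior.** If the combination is truly inside the margin, concluding non-inferiority for it is correct. The only possible false conclusion is then the second column, 9.9% to 11.5%.

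**5. Combination tested for superiority, one-sided 5%.** Independent tests give 1 − 0.90 × 0.95 = 14.5%, and ρ = 0.44 gives 13.3%. Exact enumeration, with monotherapy at 40%, the combination at 25%, and a Wald one-sided 95% limit below zero standing in for the chi-squared test, gives 13.4% (76 SelK2-only) to 15.3% (25).

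**6. Check on the power column.** The normal approximation is Φ(0.15 / √[0.1875 × (1/n + 1/76)] − 1.2816). It gives 80.3%, 73.6%, 67.8% and 58.7% for n = 76, 51, 38 and 25. If only an equal number of concurrent controls is used, n = 51, 38 and 25 give about 68%, 59% and 48%.

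**The case against.** The strongest reply is that the two contrasts concern different regimens, with separate objectives and separate sample-size hypotheses, in an open-label Phase 2 trial. Testing distinct regimens unadjusted against a shared control, and saying so in advance, is defensible. Section 2.0 also limits any claim that the sponsor could pick its primary result freely after the fact. This stands, and for that reason the point does not rest on a duty to adjust. It leaves the contradiction in place: if Section 2.0 governs, the Synopsis and Section 10.3.3 are wrong and need correcting.

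A second reply concerns the size. A reader might infer that 17-19% is this trial's error rate. The documents do not support that. The figure requires activation, and it requires that adding SelK2 to full enoxaparin raises VTE from 25% to 40%. The plan assumes 6% on the combination, and it opens the arm only if interim data suggest an additive effect. The effect of that data-driven activation on the error rate was not modelled, and the current text fixes no activation point.

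A third reply is that the combination is really meant to be tested for superiority. Section 10.1 supports this, and the figure then falls to about 13-15%. But the efficacy analysis section never states that test.

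**Conclusion.** The point holds as an inconsistency with consequences for interpretation. The analysis text allows a combination-only result to count as primary success, while the stated primary efficacy objective is monotherapy alone. It should be corrected before comparative results are used to support a claim.

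The 17-19% is a conditional upper case. It assumes activation, both regimens exactly at the margin, 76 evaluable in the combination and enoxaparin arms, and 76 down to 25 SelK2-only patients. The other two readings give about 10-11.5% (only monotherapy inferior) and about 13-15% (combination tested for superiority). Without activation there is one contrast and no issue.

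A reader might also infer that a formal adjustment is needed. It is not, once one contrast is named. Splitting alpha would have a cost: at one-sided 5%, 76 per arm gives 68.8% power, and 80% needs 104 evaluable per arm.

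**What to change.** In the Synopsis and Section 10.3.3, state three things:

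- SelK2 alone versus enoxaparin (total VTE, Treatment Phase, mITT, one-sided 10%) is the single contrast that decides the primary efficacy objective.
- SelK2 plus enoxaparin versus enoxaparin is a separate comparison for the adaptive-arm objective. It is reported with its own estimate and interval, under the test its sample size assumes (superiority, two-sided 0.1), and does not determine primary success.
- If activation closes the SelK2-only arm early, the deciding contrast will have less than the stated 80% power. With 76 controls it is about 73%, 68% and 60% for 51, 38 and 25 evaluable SelK2-only patients.

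Section 10.3.1 can stay as it is, because with one deciding contrast its statement no longer bears on the primary conclusion.

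**Cost.** A few sentences. No patients are added and no alpha is spent. The loss of power comes from closing the arm, not from the wording. The real downside for the sponsor is that a positive combination result alone could not be presented as meeting the primary objective.
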